**Assess the effect of secretin on the visibility of the pancreatic duct.**

Frequencies and rankings will be compared with Fischer exact test and Wilcoxon rank sum tests to compare visualization of the pancreatic duct pre- and post-secretin.

*Power calculation:*

To establish relationship between secreted fluid volume and subject body size or age, we base a power calculation on analysis of MR-PFT data in 19 CP patients and the assumption that secreted volume is correlated with age in this sample of patients. In a linear regression analysis of these patients, the observed residual standard error is approximately 39, with an  $R^2 \sim 0.40$ . The observed regression coefficient is 5.274, and standard deviation of predictor age is  $\sim 5.816$ . If this holds in a general population, we require at least 15 normal subjects to have a significant regression coefficient at 0.05 level, and 80% power.

Additionally, from the previously reported study of normal adult patients by Mensel et al. [25], the coefficient of variation (CV) of secreted volume (TEV in the paper) at various time points from secretin injection ranged from 0.30 to 0.51. Given that we plan to enroll subjects in two age groups (6-11.9 and 12-15.9 years old), 25 subjects in each age group will provide 80% chance that the 95% confidence interval of mean secreted volume will be within 12% to 20% of the mean value, depending on the actual CV observed.

Therefore, we plan to enroll a total of 50 evaluable subjects in the study to meet both needs above.

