**Collect normative data for pancreatic stiffness as measured by MR elastography.**

*Hypothesis 2.* Pancreatic parenchymal stiffness in the pediatric population will fall in a normative range similar to adult norms and will not depend on subject age or size. *Exp 2.* Pancreatic parenchymal stiffness will be measured in the same healthy cohort of 50 healthy pediatric subjects including 25 subjects ages 6-11.9 years and 25 subjects 12-15.9 years.

**Assess the relationship between pancreatic exocrine function, pancreatic stiffness and pancreatic parenchymal volume.** *Hypothesis 3.* Pancreatic exocrine function as measured by MR-PFT and pancreatic stiffness as measured by MRE will be dependent on pancreatic parenchymal volume. *Exp 3.* Secreted fluid volumes as measured by MR-PFT and pancreatic

stiffness as measured by MRE will be correlated with volumetric measurements of pancreatic parenchymal volume.

**Assess the effect of secretin on the visibility of the pancreatic duct.** *Hypothesis 4.* A subjective, blinded assessment of pancreatic duct visibility pre-and post-secretin will show an increase in visibility on post-secretin images.

We will also store this data to identify normative values in controls for pancreatic and any other gastrointestinal parameters in MRCP.

*Significance and Innovation:*

Our study will add significant information to the existing literature regarding diagnosis and staging of CP, and will set the foundation for using MR as a non-invasive biomarker for CP/PI in pediatrics. Our study is novel because it will investigate the use of MRI for assessing pancreatic anatomy, function, and stiffness in the pediatric population. It will also shed light on gastrointestinal anatomy and function in pediatric healthy controls which has not yet been described in the literature. Moreover, the results of our study will fill a knowledge gap regarding normal secretory function of the pancreas in children.

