### **STUDY DESIGN:**

This will be a single center prospective study of children with no history of pancreatic disease to quantify normal pancreatic volumes and secreted fluid volume (SV) in response to secretin administration as measured by MR-PFT. We will also assess the pancreatic stiffness by MR elastography as well as pancreatic duct visibility (pre-and post-secretin) in the same cohort.

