### **RECRUITMENT & CONSENT OF PARTICIPANTS:**

*Subject Recruitment:*

Recruited subjects will have no history of pancreatic disease and will be identified through review of patients presenting for non-abdominal imaging examinations. Patients presenting for musculoskeletal MRI examinations will likely be the major source for recruited patients. In the last 2 years, 1297 musculoskeletal MR examinations have been done in pediatric patients, ages 6 -15 years, at our institution, providing a ready source for recruitment. Subjects may additionally be recruited through public recruitment using existing clinical trial recruitment services at CCHMC, including advertising within our institution to raise awareness of the study. CCHMC employees may be invited to enroll their children in the study; they would be invited by the research coordinator. Subject charts will be reviewed for evidence of pancreatitis or other pancreatic disease prior to/during enrollment. Following initial screening, subjects will be contacted by the study coordinator or an investigator and enrolled after informed consent is obtained. During enrollment, absence of exclusion criteria will be confirmed with a questionnaire completed prior to imaging.

50 evaluable subjects will be recruited evenly divided as follows:

25 subjects age 6-11.9 years

25 subjects age 12-15.9 years

*Inclusion Criteria:*

1. Subjects between the ages of 6 and 15.9 years.
2. Subjects without a documented history of (or suggestive of) pancreatic disease.

*Exclusion Criteria:*

1. History of pancreatic disease, liver disease, intra-abdominal neoplasm, abdominal inflammatory process such as inflammatory bowel disease (IBD), or systemic illness that may affect pancreatic state (e.g. cystic fibrosis).
2. Subjects with surgical hardware/implanted devices making them ineligible for MRI (e.g. pacemaker or other implanted medical device not approved for MRI).
3. Subjects who require any form of sedation or general anesthesia for MRI.
4. Subjects unable to breath-hold for the required 15-20 second imaging sequence.
5. Subjects who are pregnant or less than 12 months post-partum.

*Process of obtaining Consent:*

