**STUDY PROCEDURES:**

We will contact each family prior to the MRI visit to provide information about the study. Written consent will be obtained on the day of the exam. At that time, absence of exclusion criteria will be confirmed with a questionnaire and pregnancy testing for all females of child bearing potential will be completed prior to imaging.

MR-PFT (Exp 1) and MRE (Exp 2) exams will each be performed once per subject on a 1.5T GE HDx MRI scanner (General Electric; Milwaukee, WI). Subjects will be required to fast (NPO) for four hours prior to MR imaging. Subjects will be weighed and measured immediately prior to imaging. The IV will be placed by the MRI technologist at the beginning of the imaging examination. The patient will then be placed into the scanner and the MRE passive driver will be placed on their abdomen. The patient will be provided with standard hearing protection and entertainment options (video goggles). All pre-secretin imaging will then be performed. A study team physician or a Radiology Department nurse will then inject the secretin through the IV and all post-secretin imaging will be performed. Once imaging is completed, the patient will be removed from the scanner and the IV will be removed.

Anticipated duration of MR imaging is approximately 35 minutes scan time (total 50 min in room time). Scan time pre-secretin (5 sequences, including MRE) is approximately 20 minutes. Scan time post-secretin (sequences for MR-PFT) is approximately 15 minutes. The additional time is required for positioning, localization, sequence planning, and secretin injection. The MRI examinations can be terminated at any time upon request of the participant. All MR imaging will be done as scheduled appointments.

All images will be maintained in the research PACS environment. Data that will be saved will include participant number, age at time of examination, and MR data. Identifying data will be saved in a password-protected database.

*Facilities:*

Visits will be conducted within the main clinical CCHMC Radiology Department. The MR scanner being used is owned and operated by the CCHMC Department of Radiology.

*Radiologist Review of Images:*

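### Duct visibility before and after secretin is paired within each child, but both planned tests (Fisher exact, Wilcoxon rank sum) are for independent groups

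*Combined protocol and SAP*

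**What the plan says.** The statistical section's paragraph on duct visibility is a single sentence: "Frequencies and rankings will be compared with Fischer exact test and Wilcoxon rank sum tests to compare visualization of the pancreatic duct" before and after secretin.

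Three other places settle how the two sets of readings arise.

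- Study Design says visibility is assessed "as well as pancreatic duct visibility (pre-and post-secretin) in the same cohort".
- Study Procedures describes one visit per child. All pre-secretin sequences are run first; a physician or nurse "will then inject the secretin through the IV and all post-secretin imaging will be performed".
- Purpose of Study, Hypothesis 4, states the contrast to be tested: "A subjective, blinded assessment of pancreatic duct visibility pre-and post-secretin will show an increase in visibility on post-secretin images".

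On numbers, the recruitment section says "50 evaluable subjects will be recruited evenly divided as follows", namely 25 in each of two age bands. The power calculation covers the regression of secreted volume and the precision of mean secreted volume, and concludes: "Therefore, we plan to enroll a total of 50 evaluable subjects in the study to meet both needs above". It gives no power, effect size or significance level for duct visibility. The only other Wilcoxon test mentioned is for stored anatomical data in future studies.

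**The concern.** Every child contributes a reading before and a reading after secretin, so each child is their own control. Fisher's exact test and the rank sum test treat the two sets of readings as coming from different children: 100 independent observations in place of 50 pairs. The independence assumption fails for both tests named for this hypothesis, and no paired method is named anywhere for this comparison.

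A child's duct that is easy to see before secretin is likely to be easy to see afterwards. With that positive correlation, the independent-group variance is too large for the within-child change, and p-values tend to be too large. The danger is therefore a missed effect: Hypothesis 4 could be reported as unsupported when the paired data support it.

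**Working it through.** The plan states no figure for this comparison, so there is none to reproduce. Fifty pairs come from the recruitment section. Two-sided 0.05 is assumed. Visibility rates, score scales, shifts and correlations below are assumptions.

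**1. Variance.** With proportions visible p1 (before) and p2 (after) and within-child correlation ρ, the difference in proportions has variance

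[p1(1−p1) + p2(1−p2) − 2ρ√(p1(1−p1)·p2(1−p2))] / n.

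The independent-group tests in effect set ρ = 0. For p1 = 0.6, p2 = 0.8, n = 50:

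- ρ = 0: (0.24 + 0.16)/50 = 0.0080, standard error 0.089.
- ρ = 0.5: (0.40 − 2 × 0.5 × 0.196)/50 = 0.0041, standard error 0.064.

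Under no effect (p1 = p2) the true variance is (1−ρ) times the assumed one. A nominal 5% test then has actual size of about 2[1 − Φ(1.96/√(1−ρ))]. At ρ = 0.5 this is 2[1 − Φ(2.77)] = 0.6%, before adding Fisher's own conservatism.

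**2. Example.** Visible in 30/50 before and 38/50 after, with 9 gained and 1 lost (30 − 1 + 9 = 38).

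- Fisher on 30/50 versus 38/50: p = 0.133.
- Exact McNemar on the 10 changes: 2 × (1 + 10)/2^10 = 22/1024 = 0.021.

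The correlation in this table is (29 × 11 − 1 × 9)/√(30 × 20 × 38 × 12) = 0.59.

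**3. Fisher cannot see the pairing.** Hold the margins at 30/50 and 40/50 and vary who changed:

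| Gained / lost | Fisher p | Exact McNemar p |
|---|---|---|
| 10 / 0 | 0.049 | 0.002 |
| 12 / 2 | 0.049 | 0.013 |
| 15 / 5 | 0.049 | 0.041 |
| 20 / 10 | 0.049 | 0.099 |

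The last row has a negative within-child correlation, which is unlikely here. It shows that the error can run the other way.

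**4. Simulation, visible/not visible** (50 pairs, 20,000 runs per setting).

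| ρ | No effect, 60% both times: Fisher / exact McNemar | Power, 60% to 80%: Fisher / exact McNemar |
|---|---|---|
| 0 | 3.2% / 2.9% | 52% / 50% |
| 0.3 | 1.0% / 2.7% | 52% / 66% |
| 0.5 | 0.3% / 2.5% | 52% / 83% |
| 0.6 | 0.1% / 2.2% | 51% / 93% |

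Other assumed rates at ρ = 0.5: for 50% to 70%, power is 45% versus 77%; for 70% to 85%, 29% versus 60%.

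**5. Simulation, ordinal score** (50 pairs, 4-level score cut from a normal latent variable, 4,000 runs per setting).

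| Latent correlation | No effect: rank sum / signed-rank | Power, 0.5 SD shift: rank sum / signed-rank |
|---|---|---|
| 0 | 4.7% / 4.2% | 64% / 63% |
| 0.3 | 2.0% / 4.9% | 64% / 74% |
| 0.5 | 1.0% / 5.0% | 66% / 84% |
| 0.7 | 0.2% / 4.4% | 70% / 96% |

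A 5-level score with the same shift gives 69% versus 88% at correlation 0.5 and 73% versus 97% at 0.7. The matching visible/not visible figures (Fisher versus McNemar) are 36% versus 50% and 36% versus 63%.

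**The case against.** The case on the other side accepts that the data are paired and the tests are not. It makes four points about weight.

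- **Hypothesis 4 is peripheral.** It is the last of four aims in a pilot study. The overall hypothesis concerns secreted volume and stiffness, and the sample size does not rest on duct visibility. This is correct and limits the consequence to one hypothesis. It does not make the tests suitable for it.
- **The error is conservative.** With positive correlation, a significant result from the planned tests would not be a false-positive hazard. This also stands: the charge is lost power.
- **The size is assumed.** No rate, scale, effect or correlation is given. At zero correlation nothing is lost. With a shift of a full SD at correlation 0.5, rank sum and signed-rank both have power of about 100%, and Fisher reaches 93–98% against 96–99% for McNemar. If secretin improves visibility markedly, the conclusion would rarely change. This stands as a bound: the loss matters for modest effects and for correlation clearly above zero.
- **One score per child per time is a reading of the plan.** Readers, duct segments and the post-secretin series to be scored are not specified, and several post-secretin acquisitions are listed. More scores per child would add dependence, so they would not rescue the independent-group tests. They would require a further rule alongside the replacement tests.

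**Conclusion.** The concern holds. Both tests named for Hypothesis 4 ignore the pairing that the design creates, and nothing else in the document corrects this. Under the modest effects assumed above, power falls short of the paired tests by roughly 10 to 14 percentage points at correlation 0.3 and 18 to 32 points at 0.5, for the 4-level score and the visible/not visible rates simulated here. The 5-level score and its visible/not visible version give 19 and 14 points at 0.5. There is no loss at zero correlation and little when the effect is large. Under no effect, the rank sum test rejects about 0.1% to 0.2% of the time at latent correlation 0.7, against a nominal 5%.

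These sizes rest on 50 pairs, one score per child per time, two-sided 0.05 and the stated scales and shifts. The mismatch between test and design rests on none of them. Normative ranges, sample size and the other three hypotheses are unaffected.

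**What to change.** In the duct-visibility paragraph of the statistical section:

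1. Replace the Fisher test with the exact McNemar test for visible/not visible.
2. Replace the rank sum test with the Wilcoxon signed-rank test on within-child differences in score.
3. Report the paired difference in proportion visible with its 95% confidence interval. In the example this difference is (9 − 1)/50 = 16 percentage points.
4. State that each child has one score before and one after secretin. If several readers, segments or post-secretin series are scored, state how they reduce to one score per time point, or name a model that handles the repeated scores, such as an ordinal mixed model.

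Items 1 to 3 amount to one sentence of analysis wording, and item 4 adds one line. No new data, children or readers are needed. The wording should be fixed before the images are read.

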**DATA ANALYSIS/METHODS:**

*Statistical analysis:*

Statistical analyses will be tailored to our study purposes as follows:

**Collect normative data for volume of secreted fluid in response to secretin administration in a representative sample of healthy pediatric controls.**

Means, standard deviations and 95% confidence intervals will be used to summarize study population secreted volumes. Linear regression will be used to assess for significant correlation between subject age and secreted volume. Similar regression models will be used to test other body-size covariates such as BSA, BMI, etc. If feasible, a quantile regression will be performed of secreted volume or BSA normalized secreted value to attempt to quantify normal range as a function of age, BMI, etc.

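### The figure of 15 subjects for the age regression relies on an age SD (about 5.816) that the 6 to 15.9 year eligibility range cannot produce, so 50 is borderline rather than ample for that test

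*Combined protocol and SAP*

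**What the plan says.** The Power calculation, at the end of DATA ANALYSIS/METHODS, bases its first argument on a regression of secreted volume on age in 19 CP patients. It reports that "the observed residual standard error is approximately 39, with an" R² of about 0.40, and continues: "The observed regression coefficient is 5.274, and standard deviation of predictor age is" about 5.816. From these it concludes: "If this holds in a general population, we require at least 15 normal subjects to have a significant regression coefficient at 0.05 level", with 80% power. The statement is conditional on the CP figures holding in a general population.

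A second argument covers the precision of mean secreted volume with 25 subjects per age group. The section then closes: "Therefore, we plan to enroll a total of 50 evaluable subjects in the study to meet both needs above".

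The Inclusion Criteria admit "Subjects between the ages of 6 and 15.9 years". Subject Recruitment states that "50 evaluable subjects will be recruited evenly divided as follows": 25 aged 6–11.9 and 25 aged 12–15.9. The age slope is a planned test: "Linear regression will be used to assess for significant correlation between subject age and secreted volume" (Statistical analysis, secreted volume). It also belongs to Hypothesis 1 in PURPOSE OF STUDY.

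The documents give no age SD for the children to be enrolled, and they do not adjust for the narrower age range.

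**The concern.** The power to detect a given slope depends on the spread of the predictor among the subjects actually studied. The plan carries over not only the slope and residual SD of the CP patients but also their age SD, and that last quantity is constrained by this study's own eligibility criteria. An SD of 5.816 looks too large for a range of less than ten years.

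What is at stake is how the planned 50 is read. A stated need of 15 makes 50 look like more than three times the requirement. If the margin is not there, a non-significant age slope would be misread as evidence against a relationship that the study was thought almost certain to detect.

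**Working it through.** **Inputs from the Power calculation:** slope b = 5.274 per year, residual SD s = 39, age SD 5.816, significance level 0.05, power 80%. The plan does not say whether the test is one- or two-sided; two-sided reproduces its figure.

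**Inputs from the recruitment section:** ages 6 to 15.9; strata 6–11.9 and 12–15.9, 25 subjects each.

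**Method.** Two-sided t test of a simple regression slope, n − 2 degrees of freedom, noncentrality δ = b × SD(age) × √n / s.

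**1. Reproduce the plan's figure.** b × SD / s = 5.274 × 5.816 / 39 = 0.7865. At n = 15, δ = 0.7865 × √15 = 3.046 and power is 80.4%. The 15 is reproduced. With the same inputs, n = 50 gives δ = 5.561 and power above 99.9%.

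**2. Age SD that 15 subjects need.** Solving for 80% power at n = 15 gives SD(age) = 5.788.

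**3. Age SD that eligibility allows.** The SD of values confined to an interval is at most half its width, reached with half the subjects at each end. Here that is (15.9 − 6)/2 = 4.95. Conversely, an SD of 5.788 needs a span of at least 2 × 5.788 = 11.6 years, against 9.9 available. Using the n − 1 divisor does not close the gap: the largest sample SD for 15 subjects is then about 5.11.

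**4. Best case for 15.** At SD 4.95, δ = 5.274 × 4.95 × √15 / 39 = 2.593 and power is 67%. Even there, 20 subjects are needed for 80%.

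**5. Even ages within the planned strata (assumption).** The within-stratum variances are 5.9²/12 and 3.9²/12. The stratum means are 8.95 and 13.95, each 2.5 from the overall mean. So

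SD = √{[(5.9² + 3.9²)/12]/2 + 2.5²} = 2.887.

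The implied R² is (5.274 × 2.887)² / [(5.274 × 2.887)² + 39²] = 0.13, compared with 0.38 from the same formula at SD 5.816.

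- n = 15: δ = 1.512, power 29% (28% by simulation with random ages).
- n = 50: δ = 2.761, power 77% (76% with n − 1 in place of n in δ; simulation with random ages 76–77%).
- n for 80%: 54, or 55 with n − 1.

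**6. Range over age SD, with slope and residual SD held at the plan's values.**

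| Age SD | Power at n = 50 | n for 80% power |
|---|---|---|
| 2.5 | 65% | 71 |
| 2.89 (even within strata) | 76–77% | 54–55 |
| 3.0 | 80% | 50 |
| 3.5 | 91% | 38 |
| 4.95 (maximum) | over 99% | 20 |

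Fifty subjects reach 80% only from an age SD of about 2.99.

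**7. Sensitivity to the residual SD at age SD 2.887, n = 50.** Power is 94% at a residual SD of 30, 85% at 35 and 65% at 45. Power reaches 80% if the residual SD is at most 37.65, or if the slope is at least about 5.46.

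**The case against.** The strongest reply concerns the 50, not the 15. The shortfall under even ages is about 3 points, well inside the noise of the inputs. From the plan's own figures, the standard error of the CP slope is 39 / (5.816 × √18) = 1.58, giving a 95% interval of about 1.9 to 8.6. At age SD 2.887 and n = 50 that corresponds to power from about 17% to 99%. The 95% interval for the residual SD on 17 degrees of freedom, about 29 to 58, corresponds to about 95% down to 44%. Such inputs cannot separate 77% from 80%, and the even age spread is itself an assumption. In addition, 50 has a separate basis in the precision argument for 25 per group, the study is a pilot aimed at normative data, and the plan makes its power statement conditional.

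Much of this stands. The figures for 50 depend on assumptions and should be shown as a range; they do not show that 50 is inadequate, and the precision argument is untouched. None of it rescues the 15. The condition can cover the slope and residual SD, which are unknown in healthy children, but not an age SD that the eligibility criteria exclude. The precision argument also does not support the closing sentence, which claims that the regression need is met as well. Noisy inputs are a reason to state assumptions and a range, which the plan does not do.

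**Conclusion.** The concern holds. Two conclusions need no assumption about the ages enrolled, only the plan's slope and residual SD: an age SD of 5.816 is unattainable here, and 15 subjects do not give 80% power under any permitted age distribution (at most about 67%).

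The conclusion about 50 is conditional. If the CP slope and residual SD carry over and ages are evenly spread within strata, power is about 76–77% rather than over 99.9%. Whether it reaches 80% depends on an age distribution that the plan does not state. Borderline is a fair description; the wide margin implied by the text does not exist.

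The finding covers the age regression only. The documents give no inputs for the body-size regressions. This should be fixed; confidence is high for the 15, while the exact power at 50 remains dependent on the assumptions above.

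**What to change.** In the Power calculation, delete the requirement of 15 and replace it with text such as:

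> Assuming that the slope (5.274) and residual SD (about 39) seen in 19 CP patients hold in healthy children, and that the age SD is about 2.9 (ages evenly spread within the two strata), 50 subjects give about 76–77% power for the age slope at two-sided 0.05. Power would be 65% at an age SD of 2.5, 80% at 3.0 and 91% at 3.5. Under even ages, about 54–55 subjects would be needed for 80%.

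Reword the closing sentence so that it no longer implies 80% power for the regression; the precision argument can remain as the separate basis for 25 per group. If the sponsor expects a different age mix, it should state that mix and use its SD.

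The cost is one reworded paragraph with a less favourable figure. No subjects are added and the analysis does not change.
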